13.9.2 Other Safety Considerations

Any significant worsening noted during interim or final physical examinations, electrocardiograms, X-rays, and any other potential safety assessments, whether or not these procedures are required by the protocol, should also be recorded as a non-serious or serious AE, as appropriate, and reported accordingly.

14 UNANTICIPATED PROBLEMS

14.1 Definition of Unanticipated Problems

The Office for Human Research Protections (OHRP) considers unanticipated problems involving risks to participants or others to include, in general, any incident, experience, or outcome that meets **all** of the following criteria:

- Unexpected in terms of nature, severity, or frequency given (a) the research procedures that are described in the protocol-related documents, such as the Institutional Review Board (IRB)-approved research protocol and informed consent document; and (b) the characteristics of the participant population being studied;
- Related or possibly related to participation in the research (“possibly related” means there is a reasonable possibility that the incident, experience, or outcome may have been caused by the procedures involved in the research); and
- Suggests that the research places participants or others at a greater risk of harm (including physical, psychological, economic, or social harm) than was previously known or recognized.

14.2 Unanticipated Problem Reporting

The Sponsor-Investigator will report unanticipated problems (UPs) to the reviewing Institutional Review Board (IRB).

14.3 Reporting Unanticipated Problems to Participants

Not Applicable

15 DATA REPORTING

15.1 Data submission

Electronic case report forms for study data entry will be developed by staff at the University of Miami using Velos, a HIPAA AND 21 CFR part 11 compliant database. Only investigators and assigned research staff will have access to study data. The electronic case report forms will be available to sponsor, IRB or regulatory authorities in event of an audit

15.2 Data and Safety Monitoring

The research team will continuously monitor study accruals, toxicities, and response to treatment. The Sylvester Comprehensive Cancer Center's (SCCC) Data and Safety Monitoring Committee (DSMC) will monitor this clinical trial according to the Cancer Center's data and safety monitoring (DSM) plan to assure the well-being of patients enrolled on Investigator-Initiated Trials that do not have an outside monitoring review. In its oversight capacity, the DSMC bears responsibility for suspending or terminating this study. The activities of this committee includes ongoing review of accrual, periodic review of response adverse events including SAEs, important medical events, significant revisions or amendments to the protocol, and approval of cohort/dose escalations. The DSMC also reviews reports from internal audits of protocol compliance and data integrity conducted by the University of Miami, Office of Research Compliance Assessment. If the DSMC and/or the PI have concerns about unexpected safety issues, the study will be stopped and will not resume until the issues are resolved. The DSMC will review reports from all audits, site visits, or study reviews pertaining to this clinical trial and take appropriate action. The guidelines appearing in this section are offered for DSMC consideration in assessing adverse events and response to study treatment. The SCCC DSM Plan to which this study is subject can also be found at www.sylvester.org.

15.3 Early Stopping Guidelines

We propose the following guidelines for the Sylvester Data and Safety monitoring Committee (DSMC) in its review of accumulating data on toxicity and feasibility of study treatment. The proposed guidelines were developed using Bayesian methods, which can be applied at any stage of enrollment without advance specification of the number of interim analyses to be performed, or the number of patients evaluable for toxicity, or response, at the time such assessments are made.

Under the Bayesian method, we assign a prior probability (level of belief at the start of the trial) to a range of possible values for the true toxicity rate, and likewise for the true feasibility rate. As data on treated patients become available, each of these probability distributions is revised and the resulting posterior probability becomes the basis for recommending either early termination or continuation of the study. In the sections that follow, we provide specific stopping guidelines based on posterior

probabilities for monitoring toxicity and efficacy over the course of this trial. Underlying assumptions for the prior distributions are also presented.

15.4 Early Stopping Due to Safety

The following early stopping guidelines, which are based on a Bayesian method, will be applied to ensure safety of this trial. Safety monitoring will be based on the occurrence of treatment related (possible, probable, or definite) grade 3 or higher toxicity occurring during study treatment. We suggest a stopping rule guideline for safety as a posterior probability of a rate of grade 3 or higher toxicity exceeding 20% as 90% or higher. Table 4 shows specific instances where this guideline is met. Posterior probabilities used to derive the preceding table are calculated under a prior beta distribution with parameters $\beta_1 = 0.2$ and $\beta_2 = 1.8$, which corresponds to an expected rate of 10% based on prior information roughly equivalent to having studied 2 patients. Furthermore, this prior distribution assigns a small a priori chance (17.5%) to the possibility that the true rate of unacceptable toxicity is 20% or greater.

Table 4. Stopping Rules for Safety

Number of Patients with Related Grade 3+ toxicity	Total patients Evaluated	Observed rate
3	3 to 5	>60%
4	6 to 9	>44.4%
5	10 to 12	>41.7%
6	13 to 16	>37.5%
7	17 to 20	>35%
8	21 to 24	>33.3%
9	24 to 27	>33.3%

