13.4.2 Relationship to Study Intervention

The causal relationship to study drug is determined by a physician and should be used to assess all adverse events (AE). The causal relationship can be one of the following:

Related: There is a reasonable causal relationship between study drug administration and the AE.

Not related: There is not a reasonable causal relationship between study drug administration and the AE.

The term "reasonable causal relationship" means there is evidence to suggest a causal relationship.

Adverse events can be spontaneously reported or elicited during open-ended questioning, examination, or evaluation of a subject. (In order to prevent reporting bias, subjects should not be questioned regarding the specific occurrence of one or more AEs.)

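### Table 4 safety boundary: 24 patients fall in two rows, and the `>` rates exclude counts that meet the stated posterior rule

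*Combined protocol and SAP*

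**What the plan says.** Section 15.4 recommends stopping for safety on a "posterior probability of a rate of grade 3 or higher toxicity exceeding 20% as 90% or higher". The prior is Beta(0.2, 1.8), described as a mean of 10% worth about 2 patients, with a 17.5% prior chance that the rate is 20% or more. The section introduces the boundary with "Table 4 shows specific instances where this guideline is met". Table 4 then gives, for each event count, a range of patients evaluated and an observed rate:

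| Events | Patients evaluated | Printed rate |
|---|---|---|
| 3 | 3–5 | >60% |
| 4 | 6–9 | >44.4% |
| 5 | 10–12 | >41.7% |
| 6 | 13–16 | >37.5% |
| 7 | 17–20 | >35% |
| 8 | 21–24 | >33.3% |
| 9 | 24–27 | >33.3% |

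Section 15.3 says that "the resulting posterior probability becomes the basis for recommending either early termination or continuation of the study", and that the Bayesian guidelines are ones "which can be applied at any stage of enrollment without advance specification of the number of interim analyses to be performed". Section 15.2 makes them advisory: "The guidelines appearing in this section are offered for DSMC consideration in assessing adverse events and response to study treatment".

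**The concern.** The table disagrees with itself in two ways.

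- **Rows.** Twenty-four patients belong to both of the last two rows. Every other row starts one patient after the previous row ends and gives the minimum qualifying count, so a reader will naturally take the 9-event row as meaning that nine are needed at 24.
- **Columns.** At the last number of patients in several rows, the count says the guideline is met and the `>` rate says it is not.

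Table 4 is the only place where the posterior rule is turned into counts that a committee can read off directly, and it may be consulted at any point in enrollment. Taking nine events as the requirement at 24, or requiring the strict rate as well as the count, leads to continuing when the stated rule recommends stopping.

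**Working it through.** **Inputs, all from Section 15.4.** Prior Beta(0.2, 1.8); toxicity limit 20%; posterior threshold 90%; maximum 27 patients.

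**Formula.** With x events in n patients the posterior is Beta(0.2 + x, 1.8 + n − x). The guideline is met when P(p > 0.20 | x, n) ≥ 0.90.

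**Reproducing the plan's figures.** The prior mean is 0.2/(0.2 + 1.8) = 10%. The prior P(p > 0.20) is 0.1753, matching the stated 17.5%. The smallest qualifying x is 3 for n = 3–5, 4 for 6–9, 5 for 10–12, 6 for 13–16, 7 for 17–20, 8 for 21–24 and 9 for 25–27. This matches Table 4 at every n from 3 to 27, apart from the duplicated 24.

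**The overlap at 24.**

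| n | Events | Posterior | Met? |
|---|---|---|---|
| 24 | 7 | 0.807 | no |
| 24 | 8 | 0.907 | yes |
| 24 | 9 | 0.961 | yes |
| 25 | 8 | 0.887 | no |
| 25 | 9 | 0.950 | yes |

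The minimum is 8 at n = 24 and becomes 9 at n = 25.

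**The `>` signs.** Each printed rate is the row's count over its largest n.

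| Pair | Rate | Printed | Passes `>` as printed? | Posterior |
|---|---|---|---|---|
| 3/5 | 60% | >60% | no | 0.927 |
| 4/9 | 44.44% | >44.4% | yes, by rounding only | 0.904 |
| 5/12 | 41.67% | >41.7% | no | 0.920 |
| 6/16 | 37.5% | >37.5% | no | 0.913 |
| 7/20 | 35% | >35% | no | 0.909 |
| 8/24 | 33.33% | >33.3% | yes, by rounding only | 0.907 |
| 9/27 | 33.33% | >33.3% | yes, by rounding only | 0.923 |

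All seven pairs meet the rule. The printed decimals exclude four of the 25 boundary pairs (one for each n from 3 to 27). If the cut-offs are taken as the exact fractions, a strict `>` excludes all seven. Changing to `>=` on the printed decimals would still lose 5/12. `>=` on exact fractions, read together with the row's count, fits all 25.

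The rate column cannot be used without the counts. Even with `>=` on exact fractions, it would flag 2/3 (0.869), 3/6 (0.886), 5/13 (0.893), 6/17 (0.888) and 7/21 (0.887), none of which meets the rule.

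**Effect on the chance of ever stopping.** These come from exact recursion over patients 1 to 27, with a look after every patient from the third. That look schedule is an assumption, because the plan gives none.

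| Reading of Table 4 | True rate 20% | 30% | 40% |
|---|---|---|---|
| Counts, 8 at n = 24 (the rule) | 19.1% | 58.0% | 88.5% |
| 9 required at n = 24 | 18.7% | 57.1% | 88.1% |
| Count and `>` printed decimal | 17.0% | 55.6% | 87.6% |
| Count and `>` exact fraction | 14.6% | 51.0% | 84.7% |

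Used alone, without the counts, the `>` rates move the result the other way at a true rate of 20%: 23.6% with exact fractions and 25.7% with the printed decimals.

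**Two of two.** This also meets the rule (0.932), but the table starts at three patients. Adding a look at n = 2 would give 20.5%, 58.9% and 88.8%.

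**The case against.** The best reply is that Table 4 claims only to list instances that meet the guideline. On that wording the 9-event row is true at 24 patients, because 9/24 qualifies as well as 8/24, and no row says that nine are required. The rate column is headed as an observed rate and is nowhere made a second condition. The posterior rule is itself numerical, Section 15.3 makes it the basis for the recommendation, and the guidelines are advisory. The ambiguity can therefore always be settled from the text, the effect is small, and its direction depends on how the rates are read.

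Much of this stands. The posterior does settle every case. The exact-fraction figures rest on cut-offs that are not printed, so the printed-decimal figures are the fairer measure. The missing 2/2 is an omission rather than an error.

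It does not remove the contradictions. The other six rows are consecutive ranges of minimum counts, so a repeated 24 in the seventh can only mislead. In four rows the `>` sign excludes a pair that the same row lists as meeting the guideline.

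**Conclusion.** The concern holds. The boundary is correctly derived and two of its labels are wrong: the start of the last row, and the strict inequality in the rate column.

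At true rates of 20%, 30% and 40%, requiring nine events at 24 lowers the probability of stopping by 0.4, 0.9 and 0.5 percentage points. Requiring the count and the printed rate lowers it by 2.1, 2.4 and 0.9 points. Both sets of figures assume a look after every patient from the third.

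The change is worth making because this is a decision table for patient safety, but it is a correction to the table and not to the rule.

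**What to change.** 1. Change the last row of Table 4 to 25–27.
2. Delete the rate column, or print it with `>=` as exact fractions (3/5, 4/9, 5/12, 6/16, 7/20, 8/24, 9/27), and state that the event counts, which express the posterior rule, govern.
3. State whether 2 of 2 is left out on purpose.

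A related wording point can be settled in the same edit. Section 15.4 counts "treatment related (possible, probable, or definite) grade 3 or higher toxicity occurring during study treatment", the Table 4 header reads "Number of Patients with Related Grade 3+ toxicity", and Section 13.4.2 ("The causal relationship can be one of the following") records causality only as related or not related. The three should use one scale.

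The main correction costs one table row, one column and one sentence. The stopping rule, sample size and visits are unchanged.

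### The stated safety guideline is already met at 2 related grade 3+ toxicities in 2 patients (posterior 0.932), but Table 4 has no entry below 3 patients and no minimum number is stated

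*Combined protocol and SAP*

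**What the plan says.** Section 15.4 monitors "treatment related (possible, probable, or definite) grade 3 or higher toxicity occurring during study treatment". The guideline is a "posterior probability of a rate of grade 3 or higher toxicity exceeding 20% as 90% or higher". The prior is Beta(0.2, 1.8), described as an "expected rate of 10% based on prior information roughly equivalent to having studied 2 patients", with a 17.5% prior chance that the rate is 20% or more.

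The same section states: "Table 4 shows specific instances where this guideline is met". Table 4 is captioned as the stopping rules for safety. Its first row is 3 patients with toxicity among 3 to 5 evaluated, and its last is 9 among 24 to 27. There is no row for 2 evaluated patients.

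Section 15.3 describes the Bayesian methods as ones "which can be applied at any stage of enrollment without advance specification of the number of interim analyses", and makes the posterior probability the basis for recommending termination or continuation. Section 15.2 gives the guidelines to the Data and Safety Monitoring Committee (DSMC) as advice. None of these sections sets a minimum number of evaluated patients.

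**The concern.** Table 4 is the only ready-to-use form of the rule in the protocol, and it runs without a gap from 3 to 27 patients, so a reader could take it as the whole boundary. If the written criterion can be met at a sample size that the table leaves out, two readers of the same data can reach different answers. One checks the table and finds no entry. The other computes the posterior and finds the criterion met. In practical terms, a third patient could be dosed after the protocol's own criterion has been reached.

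**Working it through.** **Inputs (Section 15.4).** Prior Beta(0.2, 1.8); toxicity threshold 20%; posterior cut-off 90%; the boundaries in Table 4.

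**Formula.** With x events in n evaluated patients the posterior is Beta(0.2 + x, 1.8 + n − x). The guideline is met when P(rate > 0.20) under that posterior is at least 0.90.

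**Step 1: reproduce the plan's own figures.** The prior mean is 0.2 / (0.2 + 1.8) = 0.10, as stated. The prior P(rate > 0.20) is 0.1753, which matches the stated 17.5%. The smallest x that meets the guideline is:

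| n | Smallest x | Posterior, first to last n |
|---|---|---|
| 3–5 | 3 | 0.983 to 0.928 |
| 6–9 | 4 | 0.977 to 0.904 |
| 10–12 | 5 | 0.962 to 0.920 |
| 13–16 | 6 | 0.966 to 0.913 |
| 17–20 | 7 | 0.959 to 0.909 |
| 21–24 | 8 | 0.954 to 0.907 |
| 25–27 | 9 | 0.950 to 0.923 |

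This agrees with Table 4 throughout. The one blemish is that n = 24 is printed in both of the last two rows, which is a separate matter.

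**Step 2: apply the same rule below n = 3.**

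- 1 of 1: Beta(1.2, 1.8), posterior 0.7425; not met.
- 1 of 2: Beta(1.2, 2.8), posterior 0.6165; not met.
- 2 of 2: Beta(2.2, 1.8), posterior 0.9316; met.

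So n = 2 is the only sample size at which the guideline can be met and Table 4 has no row.

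**Step 3: could a stricter cut-off explain the omission?** A 95% cut-off would drop 2 of 2, but it would also drop printed entries such as 3 of 5 (0.928) and 4 of 9 (0.904). The printed rows follow the 90% cut-off, and 2 of 2 passes it by more than either of those.

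**Step 4: how long the gap lasts.** If the third patient has no event, 2 of 3 gives 0.8685 and the guideline is no longer met. If the third patient has an event, 3 of 3 gives 0.983 and Table 4 applies. The gap is one look.

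**Step 5: how often it arises.** The chance that the first two patients both have an event is p²: 0.20² = 4%, 0.30² = 9%, 0.40² = 16%.

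**Step 6: effect on operating characteristics.** Exact recursion, with a check after every patient up to 27 and each outcome known before the next patient is treated:

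| True rate | Overall stopping, first check at n = 3 | Overall stopping, first check at n = 2 |
|---|---|---|
| 20% | 19.1% | 20.5% |
| 30% | 58.0% | 58.9% |

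At a true rate of 40%, the mean number of patients treated falls from 12.1 to 11.5.

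**The case against.** The strongest reply is that Table 4 does not claim to be complete. The text presents it as showing particular instances, the rule itself is the posterior probability, and the guidelines are advisory. Section 15.2 also has the research team monitoring toxicity continuously, and it provides for stopping if the DSMC or the investigator has concerns about unexpected safety issues. Section 15.3's remark about any stage of enrollment describes what the method permits; it does not order a check at n = 2.

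Much of this stands. A reader might infer that the committee would continue after 2 of 2, but the documents do not say that it will decide from the table alone, so only *could* is supportable. A reader might also infer that the table omits the most alarming signal. It does not: 2 of 2 is the earliest trigger, but 3 of 3 (0.983) and 4 of 6 (0.977) are stronger, and both are covered.

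The operating characteristics are also idealised. The event window is the whole of study treatment, up to 24 months. DSMC review is periodic, and no accrual pause is specified. Planned accrual is 27 patients in 24 to 30 months, or 27/30 = 0.9 to 27/24 = 1.1 a month. A third patient may often be dosed before both events are known, whatever the table says.

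What remains is that the caption and unbroken coverage from 3 to 27 invite use of the table as the full boundary, and nothing in the text tells a reader that smaller numbers are excluded. The provision for unexpected safety issues does not close the gap for expected toxicities.

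**Conclusion.** The point holds as a minor mismatch between a stated threshold and the table derived from it. The calculation rests only on the prior, threshold and cut-off printed in Section 15.4, all confirmed by reproducing the plan's other figures. No printed boundary is contradicted by it; one case is missing. The practical effect is limited to a single early look, and the gain in overall stopping probability (about 1.4 points at a true rate of 20% and 0.9 at 30%) is a best case because it assumes immediate knowledge of each outcome. Whether the omission is an oversight or an unstated minimum of three patients cannot be settled from the documents.

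**What to change.** Reconcile Section 15.4 with Table 4 in one of two ways, at the sponsor's choice:

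- add the entry that the stated rule implies, 2 patients with related grade 3+ toxicity among 2 evaluated; or
- state in Section 15.4 the minimum number of evaluated patients before the guideline applies, and qualify the any-stage wording in Section 15.3 to match.

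The cost is one table row or one or two sentences. Adding the row also slightly raises the chance of stopping when the true rate is only at the 20% threshold, by the 1.4 points given above. Stating a minimum leaves Table 4's present boundaries unchanged.

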15.5 Early Stopping Due to a Lack of Efficacy

Early stopping due to a lack of efficacy is built in study design since we use Simon two-stage design.

16 STATISTICAL METHODS

16.1 Statistical Hypothesis

The primary hypothesis is that the ORR in patients treated with the combination of nivolumab and BMS-986016 is significantly higher than 20%. With the null hypothesis that the ORR of 5% or lower is considered not clinically significant.

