1.6 Hypothesis

The null hypothesis is that the true response rate is 5%, it will be tested against a one-sided alternative response rate of 20%. In the first stage, 13 patients will be accrued. If there are no responses in these 13 patients, the study will be stopped. Otherwise, 14 additional patients will be accrued for a total of 27. The null hypothesis will be rejected if 4 or more responses are observed in 27 patients. This design yields a type I error rate of 0.0416 and power of 0.8011 when the true response rate is 20%

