16.2 Sample Size Determination

Based on Simon two-stage minimax design, 13 patients will be enrolled in Stage 1 and evaluated for response. If none of the 13 patients respond (CR or PR), the study will be stopped for futility. Otherwise, the study will proceed to Stage 2 and enroll additional 14 patients for a total of 27 patients. The null hypothesis will be rejected if 4 or more responses are observed among 27 patients. This design achieves 5% type I error and 80% power when the true ORR is 20%

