16.3 Statistical Analyses

Demographic and disease characteristics will be summarized using descriptive statistics. Counts and percentages will be used to summarize the distribution of categorical variables. Median, range, mean, and standard deviation will be used for continuous variables. Continuous variables will be tested using Student's t-test and/or Mann-Whitney U test. All statistical tests will be two-sided and $p < 0.05$ will be considered as statistical significance.

The full analysis set will consist of all patients enrolled. The modified full analysis set will consist of all enrolled patients, except patients withdrawn prior to the first efficacy measurement (at Cycle 2). The per-protocol analysis set will consist of all patients from the FU analysis set without any major protocol violations. The safety analysis set will consist of all patients who get treatment regardless of completion of treatment. The safety analysis set will serve as the main analysis set for safety assessments. The modified full analysis set will serve as the main analysis set for efficacy assessments. The efficacy assessment will also be performed on the per-protocol and full analysis sets.

Response rate will be estimated along with corresponding 95% confidence interval using Fisher's exact method. Tumor response (CR, PR, SD, or PD) will be defined according to RECIST v1.1 guideline. Objective response rate (ORR) will be the proportion of patients with a confirmed CR or PR and disease control rate (DCR) is calculated by the proportion of patients with confirmed CR, PR, or SD.

Progression-free survival (PFS) is defined as the time from the date of enrollment to the date that objective progression disease is documented or death due to any cause, whichever occurs first. Overall survival (OS) is defined as the time from the date of enrollment to the date of death. Duration of response is defined as the time from the date of first documented response (CR or PR) until date of documented progression or death in the absence of disease progression.

For PFS and OS, Kaplan-Meier method will be used to estimate survival rates for pre-specified time points along with 95% confidence intervals.

Safety analysis will be include detailed tabulations of adverse events by type, grade and treatment attribution.

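### Section 16.1 states 20% as the response rate to be significantly exceeded, but the null is 5% and the 4-of-27 rule supports only an ORR above 5%

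*Combined protocol and SAP*

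**What the plan says.** Four sections bear on the primary hypothesis.

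- **Section 16.1, first sentence:** "The primary hypothesis is that the ORR in patients treated with the combination of nivolumab and BMS-986016 is significantly higher than 20" per cent.
- **Section 16.1, second sentence:** "With the null hypothesis that the ORR of 5% or lower is considered not clinically significant".
- **Section 1.6:** "The null hypothesis is that the true response rate is 5%, it will be tested against a one-sided alternative response rate of 20" per cent. It also gives the two-stage rule, a type I error of 0.0416 and power of 0.8011 at a true rate of 20%.
- **Section 16.2:** "If none of the 13 patients respond (CR or PR), the study will be stopped for futility". Otherwise 14 more patients are enrolled, and "The null hypothesis will be rejected if 4 or more responses are observed among 27 patients". On error rates: "This design achieves 5% type I error and 80% power when the true ORR is 20" per cent. No null rate is given here.
- **Section 16.3:** "All statistical tests will be two-sided", with no exception named. For the primary endpoint: "Response rate will be estimated along with corresponding 95% confidence interval using Fisher's exact method".

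**The concern.** Section 16.1 is where a reader looks for the formal hypothesis, and its two sentences give two different rates. The first makes 20% the benchmark for significance. The second, like section 1.6, makes 5% the rate to be rejected.

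The decision rule is not at risk, because the counts are fixed in sections 1.6 and 16.2. The conclusion is. Someone drafting the report from 16.1 could describe a trial with 4 to 9 responses as showing an ORR significantly above 20%, which those counts cannot show. Someone holding the trial to 16.1 literally could call the same positive result a failure.

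**Working it through.** **Inputs.** Stage 1 n1 = 13, stop at 0 responses; stage 2 n2 = 14, N = 27; reject at 4 or more (sections 1.6 and 16.2). Null p0 = 5% and alternative p1 = 20% (section 1.6).

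**Step 1: reproduce the plan's figures.** With X1 the stage 1 responses and X2 the stage 2 responses,

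P(reject | p) = sum over x1 >= 1 of P(X1 = x1; 13, p) × P(X2 >= 4 − x1; 14, p),

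where the second factor is 1 once x1 >= 4.

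| Stage 1 responses | Term at p = 0.05 | Term at p = 0.20 |
|---|---|---|
| 1 | 0.35123 × 0.03005 = 0.01056 | 0.17867 × 0.55195 = 0.09862 |
| 2 | 0.11092 × 0.15299 = 0.01697 | 0.26801 × 0.80209 = 0.21496 |
| 3 | 0.02140 × 0.51233 = 0.01097 | 0.24567 × 0.95602 = 0.23487 |
| 4 or more | 0.00310 | 0.25268 |
| **Total** | **0.0416** | **0.8011** |

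(Totals are from unrounded terms.) Both match section 1.6. Enumerating two-stage designs for p0 = 5%, p1 = 20%, alpha 5% and power 80% also returns this one as the minimax design. The rule was therefore built for a 5% null, with 20% as the power point.

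**Step 2: what the smallest success shows.** 4/27 = 14.8%, which is below 20%. The observed rate cannot be significantly above a value it does not reach.

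**Step 3: what a claim of ORR above 20% would need.** Keep the stage 1 stop and compute the upper tail at a true ORR of exactly 20%:

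- P(9 or more) = 0.0736, above 0.05
- P(10 or more) = 0.0304, below 0.05

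At least 10/27 (37.0%) would be needed at one-sided 5%. Counts from 4 to 9 therefore satisfy the rule in 16.2 without supporting the first sentence of 16.1.

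**Step 4: the planned interval at the boundary.** The exact (Clopper-Pearson) two-sided 95% interval for 4/27, ignoring the two stages, is 4.2% to 33.7%. It contains 20% and also 5%.

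**The case against.** The strongest reply is that this is a slip of wording which the surrounding text corrects. The very next sentence of 16.1 gives the 5% null. Section 1.6 gives null, alternative, sidedness, rule, alpha and power in full, and 16.2 fixes the rejection count. Nobody following those sections would test against 20%, and no section plans the test that needs 10/27. This stands as far as the design and the decision go. It does not cure the text, because the statistical chapter still opens with a primary hypothesis that its own decision rule cannot establish.

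A reader might infer three stronger things, none of which the documents support.

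- **That the design is miscalibrated.** It is not: alpha and power reproduce for 5% against 20%.
- **That the primary test is two-sided, so that 4/27 might not suffice.** The two-sided sentence in 16.3 closes a paragraph on descriptive summaries and tests of continuous variables. For response rate, 16.3 plans only an estimate with an interval. Section 1.6 makes the primary test one-sided, and the specific rule governs. The sentence does literally cover all tests, so a clarifying clause is worthwhile, but no loss of power should be read into it.
- **That an interval containing 5% at 4/27 exposes an error.** A two-sided 95% interval beside a one-sided 5% test can include the null at the boundary. The plan does not make the interval the criterion of success.

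**Conclusion.** The concern holds as an inconsistency in the stated hypothesis. The first sentence of 16.1 puts the 20% power point in the place of the 5% null. Meeting the rule supports an ORR above 5%, one-sided, and nothing about exceeding 20%. The gap is between 4/27, which rejects the planned null, and 10/27, the least that would show an ORR above 20% at one-sided 5%.

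It should be fixed because it sits in the formal primary hypothesis and determines what a positive result may claim. It is at the lower end of that category, because the design and the decision are unaffected.

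The figures assume 27 patients analysed and the stage 1 stop applied as written. The interval in step 4 also assumes that the exact method named in 16.3 means Clopper-Pearson.

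**What to change.** Reword section 16.1 along these lines:

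> H0: ORR <= 5% versus H1: ORR > 5%, one-sided. The design has 80% power when the true ORR is 20%. Rejecting H0 supports the conclusion that ORR exceeds 5%.

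This is consistent with section 1.6, whose 5% is the boundary of H0 and whose 20% is the point in H1 at which power is set.

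As a minor clarification, add to the two-sided sentence in section 16.3: *except the one-sided primary Simon two-stage test*.

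Optionally, note in 16.3 that at 4/27 the two-sided 95% interval (4.2% to 33.7%) includes 5% although the one-sided rule rejects, and that this is expected.

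The cost is one reworded paragraph and one clause, plus a sentence if the optional note is taken. Sample size, boundaries, alpha, power and trial conduct do not change.
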